**Table 14.1.2. Summary of Demographic and Baseline Characteristics**

Demographic and Baseline Variables	CLL/SLL (N=xx)	MCL (N=xx)	Total (N=xx)
Age (Years)			
n	xx	xx	xx
Missing	xx	xx	xx
Mean (SD)	xx.x (xx.xx)	xx.x (xx.xx)	xx.x (xx.xx)
Median	xx.x	xx.x	xx.x
(min, max)	(xx.xx, xx.xx)	(xx.xx, xx.xx)	(xx.xx, xx.xx)
Gender			
Male	xx (xx.xx)	xx (xx.xx)	xx (xx.xx)
Female	xx (xx.xx)	xx (xx.xx)	xx (xx.xx)
Missing	xx (xx.xx)	xx (xx.xx)	xx (xx.xx)
Race			
Asian	xx (xx.xx)	xx (xx.xx)	xx (xx.xx)
Other	xx (xx.xx)	xx (xx.xx)	xx (xx.xx)
Other 1	xx (xx.xx)	xx (xx.xx)	xx (xx.xx)
Other n	xx (xx.xx)	xx (xx.xx)	xx (xx.xx)
Height (cm)			
n	xx	xx	xx
Missing	xx	xx	xx
Mean (SD)	xx.x (xx.xx)	xx.x (xx.xx)	xx.x (xx.xx)
Median	xx.x	xx.x	xx.x
(min, max)	(xx.xx, xx.xx)	(xx.xx, xx.xx)	(xx.xx, xx.xx)

- The Capital "N" in the column header represents the total number Full Analysis Set.
- The small "n" in summary statistics represents the total number of Patients.
- Percentages are based on number of patient in each group.
- SD = Standard Deviation, min=minimum, max=maximum
- Source :Listing 16.2.2.

Document Title:	Document ID:	BP04-01
Statistical Analysis Plan	Version Number:	3.1
	Effective Date:	25-Nov-2021

**Table 14.1.3. Summary of Medical and Surgical History**

System Organ Class /Preferred Term	CLL/SLL (N=xx)	MCL (N=xx)	Total (N=xx)
	n (%)	n (%)	n (%)
Patient with any medical history	xx (xx.xx)	xx (xx.xx)	xx (xx.xx)
System Organ Class 1	xx (xx.xx)	xx (xx.xx)	xx (xx.xx)
Preferred Term 1	xx (xx.xx)	xx (xx.xx)	xx (xx.xx)
Preferred Term 2	xx (xx.xx)	xx (xx.xx)	xx (xx.xx)
System Organ Class 2	xx (xx.xx)	xx (xx.xx)	xx (xx.xx)
Preferred Term 1	xx (xx.xx)	xx (xx.xx)	xx (xx.xx)
Preferred Term 2	xx (xx.xx)	xx (xx.xx)	xx (xx.xx)
System Organ Class 3	xx (xx.xx)	xx (xx.xx)	xx (xx.xx)
Preferred Term 1	xx (xx.xx)	xx (xx.xx)	xx (xx.xx)
Preferred Term 2	xx (xx.xx)	xx (xx.xx)	xx (xx.xx)
System Organ Class 4	xx (xx.xx)	xx (xx.xx)	xx (xx.xx)
Preferred Term 1	xx (xx.xx)	xx (xx.xx)	xx (xx.xx)
Preferred Term 2	xx (xx.xx)	xx (xx.xx)	xx (xx.xx)
System Organ Class 5	xx (xx.xx)	xx (xx.xx)	xx (xx.xx)
Preferred Term 1	xx (xx.xx)	xx (xx.xx)	xx (xx.xx)
Preferred Term 2	xx (xx.xx)	xx (xx.xx)	xx (xx.xx)

- The Capital "N" in the column header represents the total number Full Analysis Set.
- The small "n" in summary statistics represents the total number of Patients.
- Percentages in the "Patient with any medical history" rows are based on number of patient in each group.
- Percentages in the "System Organ Class" and "Preferred Term" rows are based on number of Patient with any medical history in each group.
- Medical histories were coded using MedDRA Ver23.0
- Source :Listing 16.2.6

Document Title:	Document ID:	BP04-01
Statistical Analysis Plan	Version Number:	3.1
	Effective Date:	25-Nov-2021

**Table 14.1.4. Summary of Concomitant Medication**

	CLL/SLL (N=xx)	MCL (N=xx)	Total (N=xx)
	n (%)	n (%)	n (%)
Visit 1			
Any concomitant medication given during visit			
Yes	xx (xx.xx)	xx (xx.xx)	xx (xx.xx)
No	xx (xx.xx)	xx (xx.xx)	xx (xx.xx)
Any prior therapy received for Chronic Lymphocytic Leukemia/ Mantle Cell Lymphoma			
Yes	xx (xx.xx)	xx (xx.xx)	xx (xx.xx)
No	xx (xx.xx)	xx (xx.xx)	xx (xx.xx)
Patient refractory to the Therapy			
Yes	xx (xx.xx)	xx (xx.xx)	xx (xx.xx)
No	xx (xx.xx)	xx (xx.xx)	xx (xx.xx)
Visit x			
Any New Concomitant medication given Since Last Visit			
Yes	xx (xx.xx)	xx (xx.xx)	xx (xx.xx)
No	xx (xx.xx)	xx (xx.xx)	xx (xx.xx)

- The Capital "N" in the column header represents the total number Full Analysis Set.
- The small "n" in summary statistics represents the total number of Patients.
- Percentages are based on number of patient in each group.
- Programme Note: Visit x- Visit 2 up to Visit 8.
- Source :Listing 16.2.19

Document Title:	Document ID:	BP04-01
Statistical Analysis Plan	Version Number:	3.1
	Effective Date:	25-Nov-2021

**Table 14.1.5. Summary of Baseline Disease Characteristics**

	CLL/SLL (N=xx)	MCL (N=xx)	Total (N=xx)
	n (%)	n (%)	n (%)
Clinical Staging (Rai Staging) of Chronic Lymphocytic Leukaemia			
Stage 0	xx (xx.xx)	xx (xx.xx)	xx (xx.xx)
Stage I	xx (xx.xx)	xx (xx.xx)	xx (xx.xx)
Stage II	xx (xx.xx)	xx (xx.xx)	xx (xx.xx)
Stage III	xx (xx.xx)	xx (xx.xx)	xx (xx.xx)
Stage IV	xx (xx.xx)	xx (xx.xx)	xx (xx.xx)
Characteristics			
Only Blood abnormality	xx (xx.xx)	xx (xx.xx)	xx (xx.xx)
Blood abnormality with lymphadenopathy	xx (xx.xx)	xx (xx.xx)	xx (xx.xx)
Blood abnormality with organomegaly	xx (xx.xx)	xx (xx.xx)	xx (xx.xx)
CLL-IPi Score			
n	xx	xx	xx
Missing	xx	xx	xx
Mean (SD)	xx.x (xx.xx)	xx.x (xx.xx)	xx.x (xx.xx)
Median	xx.x	xx.x	xx.x
(min, max)	(xx.xx, xx.xx)	(xx.xx, xx.xx)	(xx.xx, xx.xx)
Mantle Cell Lymphoma			
Relapsed	xx (xx.xx)	xx (xx.xx)	xx (xx.xx)
Refractory	xx (xx.xx)	xx (xx.xx)	xx (xx.xx)
Clinical Staging (Ann Arber)			
Stage I	xx (xx.xx)	xx (xx.xx)	xx (xx.xx)
Stage II	xx (xx.xx)	xx (xx.xx)	xx (xx.xx)
Stage IE	xx (xx.xx)	xx (xx.xx)	xx (xx.xx)
Stage IIE	xx (xx.xx)	xx (xx.xx)	xx (xx.xx)
Stage III	xx (xx.xx)	xx (xx.xx)	xx (xx.xx)
Stage IIIS	xx (xx.xx)	xx (xx.xx)	xx (xx.xx)
Stage IIIE	xx (xx.xx)	xx (xx.xx)	xx (xx.xx)
Stage IV	xx (xx.xx)	xx (xx.xx)	xx (xx.xx)
Genomic alteration			
Translocation t(11;14) (q13;q32)	xx (xx.xx)	xx (xx.xx)	xx (xx.xx)
Overexpressed cyclin D1	xx (xx.xx)	xx (xx.xx)	xx (xx.xx)
MIPI Score			
n	xx	xx	xx
Missing	xx	xx	xx
Mean (SD)	xx.x (xx.xx)	xx.x (xx.xx)	xx.x (xx.xx)
Median	xx.x	xx.x	xx.x
(min, max)	(xx.xx, xx.xx)	(xx.xx, xx.xx)	(xx.xx, xx.xx)

- The Capital "N" in the column header represents the total number Full Analysis Set.
- The small "n" in summary statistics represents the total number of Patients.
- Percentages are based on number of patient in each group.
- SD = Standard Deviation, min=minimum, max=maximum
- Source :Listing 16.2.3.

Document Title:	Document ID:	BP04-01
Statistical Analysis Plan	Version Number:	3.1
	Effective Date:	25-Nov-2021

**Table 14.1.6. Summary of Lymph Node Biopsy**

	CLL/SLL (N=xx)	MCL (N=xx)	Total (N=xx)
	n (%)	n (%)	n (%)
Lymph node enlarged			
Yes	xx (xx.xx)	xx (xx.xx)	xx (xx.xx)
No	xx (xx.xx)	xx (xx.xx)	xx (xx.xx)
Size of Lymph node (mm)			
n	xx	xx	xx
Missing	xx	xx	xx
Mean (SD)	xx.x (xx.xx)	xx.x (xx.xx)	xx.x (xx.xx)
Median (min, max)	xx.x (xx.xx, xx.xx)	xx.x (xx.xx, xx.xx)	xx.x (xx.xx, xx.xx)
Lymph node biopsy performed within 6 months before study enrolment			
Yes	xx (xx.xx)	xx (xx.xx)	xx (xx.xx)
No	xx (xx.xx)	xx (xx.xx)	xx (xx.xx)
Method of Biopsy			
Fine-needle aspiration biopsy	xx (xx.xx)	xx (xx.xx)	xx (xx.xx)
Core needle biopsy	xx (xx.xx)	xx (xx.xx)	xx (xx.xx)
Open (surgical) biopsy	xx (xx.xx)	xx (xx.xx)	xx (xx.xx)

- The Capital "N" in the column header represents the total number Full Analysis Set.
- The small "n" in summary statistics represents the total number of Patients.
- Percentages are based on number of patient in each group.
- SD = Standard Deviation, min=minimum, max=maximum
- Source :Listing 16.2.4.

Document Title:	Document ID:	BP04-01
Statistical Analysis Plan	Version Number:	3.1
	Effective Date:	25-Nov-2021

Table 14.1.7. Summary of Next Generation Sequencing\_CLL

	(N=xx)
	n (%)
Genomic sample collected for molecular cytogenetics (FISH)	
Yes	xx (xx.xx)
No	xx (xx.xx)
NA	xx (xx.xx)
Any genomic alteration observed	
Yes	xx (xx.xx)
No	xx (xx.xx)
If Yes	
11q deletion	xx (xx.xx)
13q deletion	xx (xx.xx)
17p deletion	xx (xx.xx)
12 addition	xx (xx.xx)
TP53 mutation	xx (xx.xx)
IGHV mutation	xx (xx.xx)
Other	xx (xx.xx)
Other 1	xx (xx.xx)
Other n	xx (xx.xx)

- The Capital "N" in the column header represents the total number Full Analysis Set.
- The small "n" in summary statistics represents the total number of Patients.
- Percentages in the "Genomic sample collected for molecular cytogenetics" and "Any Genomic alteration observed" rows are based on number of patient in each group.
- Percentages in the "If yes" rows are based on number of Patient Any genomic alteration observed.
- Source :Listing 16.2.5.

Document Title:	Document ID:	BP04-01
Statistical Analysis Plan	Version Number:	3.1
	Effective Date:	25-Nov-2021

Table 14.1.8. Summary of Chest X-Ray

	CLL/SLL (N=xx) n (%)	MCL (N=xx) n (%)	Total (N=xx) n (%)
Visit x			
Patient have any sign and symptom of Pneumonia			
Yes	xx (xx.xx)	xx (xx.xx)	xx (xx.xx)
No	xx (xx.xx)	xx (xx.xx)	xx (xx.xx)
Views			
Posteror anterior	xx (xx.xx)	xx (xx.xx)	xx (xx.xx)
Anteroposterior	xx (xx.xx)	xx (xx.xx)	xx (xx.xx)
Lateral	xx (xx.xx)	xx (xx.xx)	xx (xx.xx)
Assessment Result			
Normal	xx (xx.xx)	xx (xx.xx)	xx (xx.xx)
Abnormal	xx (xx.xx)	xx (xx.xx)	xx (xx.xx)
If abnormal			
Unilateral	xx (xx.xx)	xx (xx.xx)	xx (xx.xx)
Bilateral	xx (xx.xx)	xx (xx.xx)	xx (xx.xx)
If Unilateral			
Unilobar	xx (xx.xx)	xx (xx.xx)	xx (xx.xx)
Bilobar	xx (xx.xx)	xx (xx.xx)	xx (xx.xx)

- The Capital "N" in the column header represents the total number Full Analysis Set.
- The small "n" in summary statistics represents the total number of Patients.
- Percentage in the "Patient have any Sign and Symptoms of Pneumonia" rows are based on number of patient in each group
- Percentage in the "Views" rows are based on the Number of Patient have any Sign and Symptoms of Pneumonia in each group.
- Programmer Note Visit x: Visit 1 up to Visit 8
- Source :Listing 16.2.8.

Document Title:	Document ID:	BP04-01
Statistical Analysis Plan	Version Number:	3.1
	Effective Date:	25-Nov-2021

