The incidence of CLL in India is 0.41 per 100,000 person-years; not as common as in the western countries. However, estimates of the incidental cases are 5000 per year with a prevalence of 25000 patients (one-third that of the estimate for the United States)(Lad et al., 2018). In India, CLL accounts for 3-5% of all leukaemia types. CLL is a disease of the elderly and the median age of CLL presentation is >60yrs in India. The high-risk CLL is defined, by a genetic aberration of the TP53 gene [i.e., del(17p) or TP53 mutation]. The incidence of high-risk characteristics (del 17p) increase up to 50% in patients with relapsed and refractory CLL (Gogia, Gupta, Kumar, Sharma, & Soni, 2019). An Indian study showed that high-risk cytogenetic abnormalities like del(17p) and del(11q) were seen in 13.3% patients, which are more common in India than that reported in the West. (Saxena, Kumar, Sazawal, & Mahapatra, 2016)

The Scientific Expert Committee (SEC) of Oncology and Haematology, nominated by Central Drugs Standard Control Organisation (CDSCO), met on 12-Feb-2020. The committee provided recommendations to obtain marketing authorization for Acalabrutinib in the treatment of patients with CLL/SLL, and patients with MCL who have received at least one prior therapy. The marketing authorization was provided with a condition to conduct a phase IV clinical trial as per the requirements in the latest New Drug and Clinical Trial Rules (2019) in India. The phase IV trial will be a part of the marketing authorization condition, which will be issued for the additional indication of CLL for Acalabrutinib in India.

In line with the SEC recommendation and to comply with the marketing authorization condition, the current phase IV study plans to assess the safety and efficacy of Acalabrutinib in Indian patients. The data obtained from the study will help to understand the safety and efficacy profile of Acalabrutinib in Indian patients with CLL/SLL, and patients with MCL who have received at

least one prior therapy. The study will add information to currently available safety and efficacy data on Acalabrutinib.

Objectives and Endpoints

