The incidence of CLL in India is 0.41 per 100,000 person-years not; as common as in the western countries. However, estimates of the incidental cases are 5000 per year with a prevalence of 25000 patients (one-third that of the estimate for the United States). (Lad et al., 2018) In India, CLL accounts for 3-5% of all leukaemia types. CLL is a disease of the elderly and the median age of CLL presentation is >60 yrs in India. The high-risk CLL is defined, at least in part, by a genetic aberration of the TP53 gene [i.e., del(17p) or TP53 mutation]. The incidence of high-risk characteristics (del 17p) increase up to 50% in patients with relapsed and refractory CLL (Gogia et al., 2019). An Indian study showed that high-risk cytogenetic abnormalities like del(17p) and

del(11q) were seen in 13.3% patients, which are more common in India than that reported in the West. (Saxena et al., 2016)

The safety and efficacy of Acalabrutinib in previously untreated CLL were evaluated in a randomised, multi-centre, open-label Phase 3 study (ELEVATE-TN) of 535 patients. Patients received Acalabrutinib plus Obinutuzumab, Acalabrutinib monotherapy, or Obinutuzumab plus Chlorambucil. Patients 65 years of age or older or between 18 and 65 years of age with coexisting medical conditions were included in ELEVATE-TN. The trial also allowed patients to receive antithrombotic agents other than warfarin or equivalent vitamin K antagonists. (PI, 2020)

Patients were randomised in a 1:1:1 ratio into 03 arms to receive

- Acalabrutinib plus Obinutuzumab (Acalabrutinib+G): Acalabrutinib 100 mg was administered twice daily, starting on Cycle 1 Day 1 until disease progression or unacceptable toxicity. Obinutuzumab was administered starting on Cycle 2 Day 1 for a maximum of 6 treatment cycles. Obinutuzumab 1000 mg was administered on Days 1 and 2 (100 mg on Day 1 and 900 mg on Day 2), 8 and 15 of Cycle 2 followed by 1000 mg on Day 1 of Cycles 3 up to 7. Each cycle was of 28 days.
- Acalabrutinib monotherapy: Acalabrutinib 100 mg was administered twice daily until disease progression or unacceptable toxicity.

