- Obinutuzumab plus Chlorambucil (GClb): Obinutuzumab and Chlorambucil were administered for a maximum of 6 treatment cycles. Obinutuzumab 1000 mg was administered on Days 1 and 2 (100 mg on Day 1 and 900 mg on Day 2), 8 and 15 of Cycle 1 followed by 1000 mg on Day 1 of Cycles 2 up to 6. Chlorambucil 0.5 mg/kg was administered on Days 1 and 15 of Cycles 1 up to 6. Each cycle was of 28 days.

Patients were stratified by 17p deletion mutation status (presence versus absence), ECOG performance status (0 or 1 versus 2), and geographic region (North America and Western Europe versus other). After confirmed disease progression, 45 patients randomised on the GClb arm crossed over to Acalabrutinib monotherapy.

The primary endpoint was progression-free survival (PFS) as assessed by an Independent Review Committee (IRC) per iwCLL 2008 criteria with the incorporation of the clarification for treatment-related lymphocytosis (Cheson 2012). With a median follow-up of 28.3 months, PFS by IRC indicated a 90% statistically significant reduction in the risk of disease progression or death for previously untreated CLL patients in the Acalabrutinib + G arm compared to the GClb arm. At the time of analysis, median overall survival had not been reached in any arm with a total of 37 deaths: 9 (5%) in the Acalabrutinib +G arm, 11 (6.1%) in the Acalabrutinib monotherapy arm, and 17 (9.6%) in the GClb arm.

PFS results for Acalabrutinib with or without Obinutuzumab were consistent across subgroups, including high-risk features in the high-risk CLL population (17p deletion, 11q deletion, TP53 mutation, and un-mutated IGHV), the PFS hazard ratios of Acalabrutinib with or without Obinutuzumab versus Obinutuzumab plus Chlorambucil were 0.08 [95% CI (0.04, 0.15)] and 0.13 [95% CI (0.08, 0.21)], respectively.

Patients with CLL who received at least one prior therapy (PI, 2020)

The safety and efficacy of Acalabrutinib in relapsed or refractory CLL were evaluated in a randomised, multi-centre, open-label phase 3 study (ASCEND) of 310 patients who received at

least one prior therapy. Patients received Acalabrutinib monotherapy or Investigator's choice of either Idelalisib plus Rituximab or Bendamustine plus Rituximab. The trial allowed patients to receive antithrombotic agents other than warfarin or equivalent vitamin K antagonists.

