Patients were randomised 1:1 to receive either: Acalabrutinib 100 mg twice daily until disease progression or unacceptable toxicity, or Investigator's choice:

- Idelalisib 150 mg twice daily until disease progression or unacceptable toxicity in combination with ≤ 8 infusions of rituximab ($375 \text{ mg/m}^2/500 \text{ mg/m}^2$) on Day 1 of each 28-day cycle for up to 6 cycles
- Bendamustine 70 mg/m^2 (Day 1 and 2 of each 28-day cycle) in combination with rituximab ($375 \text{ mg/m}^2/500 \text{ mg/m}^2$) on Day 1 of each 28-day cycle for up to 6 cycles

Patients were stratified by 17p deletion mutation status (presence versus absence), ECOG performance status (0 or 1 versus 2), and a number of prior therapies (1 to 3 versus ≥ 4). After confirmed disease progression, 35 patients randomised on the Investigator's choice of either Idelalisib plus Rituximab or Bendamustine plus Rituximab crossed over to Acalabrutinib.

The primary endpoint was PFS as assessed by IRC iwCLL 2008 criteria with the incorporation of the clarification for treatment-related lymphocytosis (Cheson 2012). With a median follow-up of 16.1 months, PFS indicated a 69% statistically significant reduction in the risk of death or progression for patients in the Acalabrutinib arm. At the time of analysis, median overall survival had not been reached in any arm with a total of 33 deaths: 15 (9.7%) in the Acalabrutinib monotherapy arm and 18 (11.6%) in the Investigator's choice of either Idelalisib plus rituximab or Bendamustine plus rituximab arm.

PFS results for Acalabrutinib were consistent across subgroups, including high-risk features. In the high risk CLL population (17p deletion, 11q deletion, TP53 mutation, and un-mutated IGHV), the PFS HR was 0.27 [95% CI (0.17, 0.44)].

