4.1.1 Screening Phase (Visit 1)

Patients, or their Legally Acceptable Representative (LAR), will provide written informed consent before any trial-specific procedures are performed. If the patient and/or LAR are unable to read, an impartial witness should be present during the entire informed consent discussion. During the Screening Phase, eligibility criteria will be reviewed, and a complete clinical evaluation will be performed as specified in the SoA (Table 1). Screening procedures will be performed up to 07 days prior to Cycle 1, Day 1. All baseline disease characteristics will be captured based on the evaluation performed as a part of routine clinical practice. The investigations that are required before the consideration of the patient for Acalabrutinib treatment must have been performed before the first dose (Cycle 1, Day 1). The NGS tests should be performed before the start of the treatment as per SoA (Table 1). Next-generation sequencing will be conducted to understand the genetic profile in Indian settings. Molecular cytogenetics (FISH) for del(13q), del(11q), del(17p), trisomy 12 in peripheral blood lymphocytes; TP53 mutation; immunoglobulin variable heavy chain (IGHV) mutational status will be assessed before the start of treatment in CLL/SLL-naïve patients, or CLL/SLL patients who did not have their report. However, MCL patients are Relapsed/Refractory and their previous report data will be used. A six months old report can be considered for both the conditions.

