**Listing 16.2.5. Listing of Patient Next Generation Sequencing-CLL**

Patient Number	Genomic sample collected for molecular cytogenetics (FISH)	Date of sample	Any genomic alteration observed	Specify the alterations	Other, specify
xx-xxxx	Yes/No/NA	DD-MMM-YYYY	Yes/No	xxxx	xxxx
xx-xxxx	Yes/No/NA	DD-MMM-YYYY	Yes/No	xxxx	xxxx
xx-xxxx	Yes/No/NA	DD-MMM-YYYY	Yes/No	xxxx	xxxx
xx-xxxx	Yes/No/NA	DD-MMM-YYYY	Yes/No	xxxx	xxxx
xx-xxxx	Yes/No/NA	DD-MMM-YYYY	Yes/No	xxxx	xxxx

Document Title:	Document ID:	BP04-01
Statistical Analysis Plan	Version Number:	3.1
	Effective Date:	25-Nov-2021

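### SAP Table 14.1.7 reports IGHV only as mutated and counts it as a genomic alteration, so un-mutated IGHV cannot be read or told from not tested

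*SAP*

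**What the plan says.** **Purpose and scope of testing.** Protocol 4.1.1 states that "Next-generation sequencing will be conducted to understand the genetic profile in Indian settings". It lists FISH for four chromosomal abnormalities, TP53 mutation and IGHV mutational status, to be assessed before treatment in treatment-naïve CLL/SLL patients and in other CLL/SLL patients without a report. A report up to six months old is accepted. The Schedule of Activities footnote says the same.

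**High-risk features.** Protocol 2.2.2, on the treatment-naïve phase 3 trial, refers to "high-risk features in the high-risk CLL population (17p deletion, 11q deletion, TP53 mutation, and un-mutated IGHV". For the relapsed or refractory phase 3 trial it gives the same four: "In the high risk CLL population (17p deletion, 11q deletion, TP53 mutation, and un-mutated IGHV), the PFS HR was 0.27". The Synopsis is narrower: "The high-risk CLL is defined, by a genetic aberration of the TP53 gene [i.e., del(17p) or TP53 mutation". The background version of that sentence is qualified: "The high-risk CLL is defined, at least in part, by a genetic aberration of the TP53 gene". Both sections cite 13.3% of Indian patients with high-risk abnormalities such as del(17p) and del(11q).

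**The shells.** SAP Table 14.1.7 asks whether any alteration was observed and, for those answering yes, gives rows for 11q, 13q and 17p deletion, an added chromosome 12, TP53 mutation, "IGHV mutation" and other findings. Its footnote says the percentages in these "rows are based on number of Patient Any genomic alteration observed". Listing 16.2.5, the table's source, has a column for "Any genomic alteration observed" and free fields to specify what was found. It has no column for IGHV status or for whether IGHV was tested. The SAP text describes no other genetic analysis, so these shells are the specification.

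**The concern.** IGHV status has two levels, and the one the protocol associates with higher risk is un-mutated. The table shows the other level and treats it as a lesion alongside del(17p) and TP53 mutation. Followed as written, a patient with mutated IGHV alone is a yes for any alteration. A patient whose only notable result is un-mutated IGHV has no row and would fall under no, next to patients never tested for IGHV.

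Two printed results are affected: the IGHV distribution itself, and the percentages for the other lesions, whose denominator changes with the number of mutated-only patients. The trial has a single arm, so its response results will be read against earlier trials, and the baseline genetic mix is part of that reading.

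**Working it through.** The plan states no IGHV figure to reproduce. The inputs from the documents are the planned 90 CLL/SLL and 10 MCL patients, the 13.3% Indian figure, and the table's rows and denominator rule. All other counts below are assumptions for illustration.

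**1. Can un-mutated IGHV be recovered?** Let *m* be the printed mutated count and *T* the number with an IGHV result. Then un-mutated = *T* − *m*, and *T* is not reported. The row for a collected sample does not supply it, because that row concerns FISH, and an existing report can replace a new sample. With *m* = 36:

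| *T* | Un-mutated | Share of tested |
|---|---|---|
| 36 | 0 | 0% |
| 60 | 24 | 40% |
| 72 | 36 | 50% |
| 90 | 54 | 60% |

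The documents give no frequency for mutated IGHV. If it were 30% to 60% of 90, *m* would be 27 to 54, and the upper limit for un-mutated would be 90 − 27 = 63 down to 90 − 54 = 36. The lower limit stays at 0 throughout.

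**2. What does this do to a four-feature count?** Suppose 20 of 90 patients have del(17p), del(11q) or TP53 mutation, and *U* are un-mutated. The number with at least one of the four features lies between max(20, *U*) and 20 + *U*:

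- *U* = 0: 20 (22%)
- *U* = 27: 27 to 47 (30% to 52%)
- *U* = 54: 54 to 74 (60% to 82%)

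The two-feature count from the Synopsis definition, del(17p) or TP53 mutation, does not depend on *U*.

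**3. What does the denominator rule do?** Suppose 12 CLL/SLL patients have del(17p) or del(11q). Of the cohort this is 12/90 = 13.3% (Clopper-Pearson 95% interval 7.1% to 22.1%). The table would instead divide by the number with any alteration. Suppose 45 patients have an alteration other than mutated IGHV, and add those with mutated IGHV only:

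| Mutated-only patients added | Denominator | Printed share |
|---|---|---|
| 0 | 45 | 26.7% |
| 10 | 55 | 21.8% |
| 20 | 65 | 18.5% |
| 30 | 75 | 16.0% |

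The lesion count is 12 in every line; only the number of mutated-only patients differs. The first line shows that the denominator rule alone already prevents comparison with 13.3%. The IGHV row then moves the percentage further, by an amount the reader cannot see. The table's single column also defines N as the Full Analysis Set without saying that MCL patients are excluded. If all 100 were the base, the same 12 would be 12.0%.

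**The case against.** A reader might infer that the table reports the wrong category and cannot show how far the Indian cohort is enriched for high-risk CLL. The documents do not support that. The Synopsis defines high risk by del(17p) or TP53 mutation, and both have rows. The 13.3% figure concerns del(17p) and del(11q), and both have rows. The four-feature list describes subgroups of earlier trials and is not adopted as this study's definition. Mutated is also a legitimate level of IGHV status, so the row is incomplete rather than wrong.

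Nor can the any-alteration count be called an inflated high-risk count. The block also holds 13q deletion, an added chromosome 12 and other findings, none of which is among the four features. It is a general genetic profile.

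It can further be said that the listing's free-text fields could hold an un-mutated result, that the row label might be shorthand for status, and that the eCRF is not among the documents. This is fair as far as it goes. However, nothing in the shells requires un-mutated or not tested to be recorded, and the SAP gives no coding rule, so two programmers could produce different tables.

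Finally, there is no genetic objective, no hypothesis test and no planned analysis by genetic risk, and Table 14.1.5 also describes risk through Rai stage and the CLL-IPI score. That limits the consequence. It does not supply the missing IGHV level or the number tested.

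**Conclusion.** The point holds in a limited form. As specified, un-mutated IGHV cannot be read from Table 14.1.7, and neither the table nor Listing 16.2.5 separates it from not tested. Mutated-only patients enter both the any-alteration count and the denominator of the individual lesion percentages, so those percentages cannot be set beside the 13.3% figure.

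The sizes shown rest on assumed counts; the direction and the loss of information follow from the shells alone. Counts of del(17p), del(11q) and TP53 mutation survive and can be re-based by hand on the column total, though not on patients tested. This is a descriptive baseline table. For IGHV the stated purpose of the testing is not met, but the primary safety analysis does not change.

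**What to change.** In Table 14.1.7 and Listing 16.2.5:

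1. Take IGHV out of the any-alteration block.
2. Report IGHV status separately as mutated, un-mutated, or not tested or not determinable.
3. Base the IGHV percentages and each individual-alteration percentage on CLL/SLL patients with a result for that test, print that number, and label the column as CLL/SLL.

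A composite high-risk row is optional. If one is added, it must state whether it uses the Synopsis definition or the four features in Protocol 2.2.2, because the two give different counts.

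The cost is a change to one table shell and one listing shell, and at most one eCRF field, filled from the IGHV report the protocol already requires. No new sample or visit is needed.
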